6. INCLUSION AND EXCLUSION CRITERIA*

Patient Subjects:

Inclusion Criteria:

- Age 18 years or older
- Patients must be preparing for discharge from the emergency department after being treated for either hyperglycemia or hypoglycemia
- Patients must be either new referrals to the DCOE or existing DCOE patients in need of post-ED follow up
- Patients must have type 1 or type 2 diabetes
- Patients must be able to provide informed consent
- Patients must be fluent in English or Spanish

Exclusion Criteria:

- Current CGM use
- Need for hospital admission
- Upcoming computed tomography (CT) or magnetic resonance imaging (MRI) studies within 2 weeks, as these imaging modalities could potentially affect CGM performance
- Pregnant patients, as the device is not approved for pregnancy
- Any altered mental status, which would limit a patient's ability to consent to the study
- Patients who already have a longitudinal relationship with an outside endocrinologist
- Patients who have not been referred to the DCOE
- Prisoners
- Patients under age 18 years
- Patients who do not speak English or Spanish fluently

Justifications for Criteria:

-Our intervention targets patients with diabetes who are treated and discharged from the emergency department after being treated for either hyperglycemia or hypoglycemia.

-We will translate consent materials and patient instructions into Spanish. No additional languages are included as the CGM being used for the study and its associated reader only has English and Spanish menus and instructional manuals.

-Prisoners represent a special population that is routinely excluded from similar research studies. They represent an inaccessible population.

-Patients under eighteen are typically treated by pediatric endocrinologists and have different care regimens that are beyond the scope of this study.

-Pregnant women will not be included in this arm of the study as the CGM being utilized for this study is not FDA approved for use in pregnant women.

Provider Subjects:

Inclusion criteria for provider subjects will consist of licensed independent providers (NP, PA, MD, DO or MBBS) who provide subspecialty diabetes care to a patient subject enrolled in the study. Pregnant women may be included in this cohort as this study arm entails less than minimal risk and the study activities have no impact on pregnancy.

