9. STUDY TIMELINES*

Patient Subject Participant Involvement Timeline:

- ***Enrollment & Intake Visit: (Day 0)***
 - Informed consent
 - Non-biometric data – Contact information; Intake data points
 - Five-question Problem Areas in Diabetes (PAID-5) scale as well as the 17-question Diabetes Distress Scale (DDS) and supplemental questions will be administered
 - Device training (if randomized to CGM)

- Care coordination to DCOE (all patients)
- ***Outpatient Blood Sugar Monitoring (for intervention group only) (day 0-14)***
 - Continuous Glucose Monitoring – Sensor worn 24 hours a day for up to 14 days.
Data can be uploaded
- ***Follow Up: (~Day 14-21 post ED visit)***
 - Study team will meet patient at follow-up appointment
 - Biometric data – Downloaded
 - Non-biometric data – Five-question Problem Areas in Diabetes (PAID) scale as well as the 17-question Diabetes Distress Scale (DDS) and supplemental survey questions will be administered
 - Compensation (\$10)
- ***6 Months Follow up (no active patient involvement)***
 - Follow-up data points abstracted from electronic health record (EHR)

Provider Subject Participant Involvement Timeline:

- ***Follow Up: (~Day 14-21 post ED visit of patient subjects)***
 - Study team send survey questions to provider subjects immediately after they have a clinic encounter with a patient subject
 - This will be the only time point of participation for provider subjects

Study Timeline: We anticipate that recruitment will be complete by September 30, 2022. Primary data analysis will be complete by the end of March 2023.

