11. PROCEDURES INVOLVED*

Enrollment & Intake Visit of patient subjects:

- **Recruitment:** See Section 24. Research personnel will confirm subjects' pregnancy status by subject self report.
 - **Documents:**
 - **HIPAA Waiver**
 - **Info Sheet**
 - **Screening Log**
 - **Declined/Ineligible Log**
- **Consent:** See Sections 30 & 31
 - **Documents:**
 - **Consent**
 - **HIPAA Authorization**
- **Randomization:** Using the Redcap randomization module, patients will be randomized to the care coordination-only or care coordination plus CGM group
- **Master Code Contact Information:** Study Staff will obtain at least two ways (primary phone number and mailing address) to contact participants to schedule follow-up visits, completing a follow-up phone call if necessary, and to ensure the CGM equipment is returned.
 - **Documents:**
 - **Contact Info**
 - **Master Code**
- **Intake:** Study Staff will query EMRs to obtain the data points listed in the document below. Data collected will be verified with participants.
 - **Documents:**
 - **Intake Data- RA Facing**
 - **Intake Data- Patient Facing**
- **Device Training for intervention arm (CGM Arm only):** Half of the participants identified and enrolled as described above will be randomized to receive an unblinded CGM. We plan to use the 14-day Libre 2 CGM from Abbott. This device is a small disk (1.38 inches in diameter and 0.2 inches thick), and it weighs 0.18 ounces. After it is placed, a small (less than 0.4mm thick) sensor probe (not sharp) remains in the skin and can transmit continuous glucose data to a reader. The device can be submerged in water, and if it falls off, there will not be any significant bleeding. Study Staff will demonstrate the features and use of the CGM and sensor application (how the device should be worn, when it should be removed, the procedure to query the device for blood sugar readings using either a reader or smart phone application). After participants demonstrate an understanding of the use of the GCM, Study Staff will place the device on one of the participant's upper arms (patient choice) and monitoring will begin immediately after a

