- **Diabetes Center of Excellence Care Coordination:** Study Staff will follow up with ED provider to ensure that patients' have clinically indicated referral to diabetes center of excellence

→ **Appointment scheduling:** RA will make an appointment for the patient before ED discharge, if possible. If this is not possible, RA will contact the patient after discharge to arrange a follow-up appointment.

Outpatient Blood Sugar Monitoring: The CGM will be worn on the participants' upper arm continuously for 14 days (or until it falls off or the patient decides to remove it)

[figure not shown]
Visit #1 (~Day 14-21 Post-Discharge of patient subjects)

- **Documents:**
 - **Visit Data (RA facing)**
 - **Problem Areas in Diabetes (PAID-5) scale/Diabetes Distress Scale and supplemental questions**
 - **Fact sheet for provider subjects**
 - **Provider satisfaction survey**
- **CGM Data:** Biosensor data will be downloaded and reviewed
- **Material Collection:** Study Staff will collect CGM readers
- **Compensation:** Participants will be offered \$10 worth of gift cards to a retail store for completing visit #1.
- **Provider Survey:** immediately following an encounter with a patient subject, the provider taking care of each patient will be contacted by the study team as potential provider subjects. Potential provider subjects subsequently will be sent an email solicitation to participate in a Redcap survey. A fact sheet will be provided with that email. The survey will consist of 4 questions pertaining to their satisfaction with patient subject care coordination and/or their CGM utilization. Providers may be sent multiple surveys if they see multiple subjects who are enrolled in the study. This is the only involvement of the provider subjects.
- **No Shows:** *RAs will reach out to subjects who miss their follow-up appointment to (1) help them reschedule and (2) ask that they fill out the post-intervention questionnaire via an online link (or mailed paper copy or via phone, if desired)*

Follow up Data Collection (~6 months Post-Discharge)

- **Documents:**
 - **6 month follow up datasheet**
- **Data Collection:** The study team will query the EHR to collect follow up data points about enrolled subjects

Figure 1: Procedural Flow Sheet

t

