Sample Size: The primary outcomes are the clinic attendance rate and the change in diabetes-related distress, as measured by the Diabetes Distress Scale (DDS) and PAID-5 scale between the ED visit and the follow-up appointment date (19). Secondary outcomes include repeat ED/EMS utilization over 6 months, repeat hospitalizations, major cardiovascular events, and changes in hemoglobin A1c. For clinic attendance, we will aim to achieve attendance at 80% of the scheduled clinic visits. For a one-sided test at alpha=0.025 of a single proportion against a standard proportion (0.80), we will have 80% power to detect a difference of 0.13 (0.80 – 0.67) with a sample size of 83 subjects in the CGM group. Adjusted for 20% dropout, we will need approximately 100 subjects/group. For the DDS outcome, we will compare the change from baseline to the end of follow-up in the DDS between the two groups. Although we will fit the trajectory of the DDS change in each group using all DDS measures in a mixed effects model with repeated measures (MMRM), for simplicity in sample size estimation, we will calculate the sample size for an unadjusted comparison of the change between the two treatment groups. Based on a study of 267 subjects with diabetes (19), the standard deviation of the DDS was 1.0 across the three sites in that study. The DDS is a questionnaire of 17 questions, each scored on a Likert scale of 1 (not a serious problem) to 6 (serious problem), with the overall score calculated as the mean score across the 17 items. Thus, the range of the overall score is 1.0 – 6.0. With 100 subjects in each group, we can detect a difference of about 0.40 in the DDS change between the two groups. The literature on the DDS does not identify a clinically meaningful difference although Fisher, Polonsky, Hessler, Mullan (2012) suggest a difference of 0.5 as meaningful (20). Thus, our sample size will achieve power of greater than 80% to detect that difference.

Analysis Strategy: As indicated in the Sample Size section above, for the clinic attendance rate, we will conduct the initial unadjusted analyses using an exact test of the frequencies under the presumed population proportion (0.80) and the observed proportion. Adjusted analyses will be conducted using a logistic regression model for the proportion of clinic visits attended as the outcome in the intervention group with predictors including age, gender, time since diagnosis of diabetes, and other factors of interest.

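### As listed, the follow-up visit is booked after randomisation, at staff discretion and with no concealment of the arm, so attendance could shift through uneven booking effort even if CGM has no effect

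*Combined protocol and SAP*

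**What the plan says.** **Order of steps.** The intake list in Section 11 goes from recruitment to consent to randomisation: "Using the Redcap randomization module, patients will be randomized to the care coordination-only or care coordination plus CGM group". Contact details, intake data, CGM training and placement, reader set-up, education and questionnaires follow. Referral confirmation and booking come last. In Section 9 the Day 0 list places "Care coordination to DCOE (all patients" after device training.

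**How booking works.** Section 11: "RA will make an appointment for the patient before ED discharge, if possible". Failing that, the RA contacts the patient after discharge. No number or timing of attempts is given. RAs also help patients who miss the visit to reschedule, and the plan does not say whether a rescheduled visit counts as attended.

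**Who does it.** Section 23 gives the RA role both CGM training and the arranging of follow-up visits. The CGM is unblinded and fitted in the ED. No section keeps the scheduler unaware of the arm.

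**Referral.** Section 6 excludes "Patients who have not been referred to the DCOE". Section 24 has staff ask the treating physician about an intended referral before the patient is approached.

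**Outcome and analysis.** Attendance is a co-primary outcome. Sections 4 and 10 hypothesise a lower no-show rate with CGM than with care coordination alone. Section 13 sets its 80% target over scheduled visits. It specifies an exact one-sample test against 0.80 and a logistic model in the intervention group.

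**The concern.** Care coordination is the background against which CGM is to be assessed, so it has to be delivered alike in both arms. As listed, the step of it closest to the attendance outcome is carried out when the arm can be known, and with latitude over whether the visit is secured before the patient leaves.

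The protocol also gives staff a reason, specific to one arm, to secure the visit. Readers are collected and sensor data downloaded at Visit 1, and contact details are taken partly so that equipment comes back (Section 11). If CGM patients were booked more reliably for that reason, their attendance would rise without the glucose data having done anything. Booking happens after randomisation, so adjusting for it in the analysis would not restore a clean comparison.

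Two other features add to the exposure. Rescheduling of missed visits rests with the same role. And a denominator of scheduled visits can leave out patients who were never booked.

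**Working it through.** **1. The plan's own figure.** Section 13 gives 80% power "with a sample size of 83 subjects in the CGM group" for a one-sided one-sample test at 0.025, with proportions 0.80 and 0.67.

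n = [(z₀.₉₇₅·√(p₀(1−p₀)) + z₀.₈₀·√(p₁(1−p₁))) / (p₀−p₁)]²

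= [(1.960 × 0.400 + 0.842 × 0.470) / 0.13]² = 82.35, rounded up to 83.

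The figure reproduces. It shows that the 13 points are a contrast between the CGM group and a fixed standard. They are not a planned difference between arms. Nothing below depends on this calculation or changes N.

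**2. Opportunity, from the text.**

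| Condition | Where | Status |
|---|---|---|
| Booking listed after allocation or CGM training | Sections 9 and 11 | Read from list order in both |
| Booking discretionary | Section 11 | Stated |
| One role trains on CGM and books | Section 23 | Stated for the role |
| Arm concealed from the scheduler | None | No such provision |

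**3. Possible size, with assumed inputs.** The documents give no booking rates and no attendance by type of booking. Assume that CGM has no effect, that attendance is 80% if the visit is booked before discharge and u otherwise, and that a share b of an arm is booked before discharge. Then:

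attendance = 0.80·b + u·(1−b)

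false difference = (b_CGM − b_control) × (0.80 − u)

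Take b_CGM = 90%. Each cell gives the false difference in points. In brackets is the chance that a pooled two-proportion z-test (two-sided 5%, 100 per arm as in Section 25) rejects.

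| u | b_control = 80% | b_control = 70% | b_control = 60% |
|---|---|---|---|
| 70% | 1 (5.3%) | 2 (6.3%) | 3 (8.0%) |
| 60% | 2 (6.3%) | 4 (10.1%) | 6 (16.5%) |
| 50% | 3 (7.8%) | 6 (16.2%) | 9 (29.6%) |
| 40% | 4 (9.9%) | 8 (24.2%) | 12 (45.7%) |

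The largest cell in full:

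- CGM arm: 0.9 × 0.80 + 0.1 × 0.40 = 0.76.
- Control arm: 0.6 × 0.80 + 0.4 × 0.40 = 0.64.
- Difference 0.12; pooled rate 0.70.
- SE under the null: √(0.70 × 0.30 × 2/100) = 0.0648.
- SE at the two rates: √(0.76 × 0.24/100 + 0.64 × 0.36/100) = 0.0642.
- Upper-tail rejection: 1 − Φ((1.96 × 0.0648 − 0.12)/0.0642) = 0.456. The lower tail adds almost nothing; the unrounded total is 45.7%.

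**4. What this does to the specified analysis.** Section 13 does not specify a between-arm test of attendance, so the bracketed rates apply only to a comparison made to address the hypothesis in Sections 4 and 10. In the one-sample test the effect is direct. In the same cell, the CGM arm would attend at 76%, where it would have attended at 64% with the control arm's booking rate. The test has no means of separating that shift from an effect of CGM.

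**The case against.** **The order is only a list order.** No sentence says that booking must follow randomisation, and the lists do not agree in every respect: Section 9 puts the questionnaires before device training, Section 11 after it. Section 4 mentions referral and scheduling before it mentions the CGM. Figure 1, the procedural flow sheet, could not be read in the text available and may settle the matter. What stands is that the order is inferred. But both lists put care coordination after device training, Section 4 describes programme components without setting a sequence, and no readable text puts booking first.

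**Stronger readings that the documents do not support.**
- A reader might infer that one and the same RA fits the sensor and then books the visit. Section 23 describes a role, and Section 11 says study staff for training and placement.
- A reader might infer that CGM patients wait in the ED through the 60-minute calibration, leaving more time to book. Section 11 says only that monitoring starts after it. Training also occupies staff, so the bias could run either way.
- A reader might set a 3 to 6 point false difference (the u = 50% row) against the 13 points in Section 13. Step 1 of the working shows that those points are not a between-arm effect, so the share means nothing.
- A reader might infer that patients are commonly randomised and then found ineligible for want of a referral. Section 24 largely settles the intention to refer before approach, and Section 4 has a referral placed only where necessary. Late confirmation is a minor residual matter.

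**The size is assumed.** That is correct. The mildest cell is 1 point, with rejection close to the nominal 5%.

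**Conclusion.** The concern holds in a limited form. As listed, a discretionary step of the shared care, closely tied to a co-primary outcome, comes after allocation and is open to staff who may know the arm. That creates an opportunity for bias in the CGM-arm attendance rate and in any comparison of no-show rates between arms. The documents do not show that booking would in fact be uneven, nor in which direction.

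The range of 1 to 12 points, with between-arm rejection of about 5% to 46%, rests wholly on the assumed rates and on CGM having no effect. Confidence that the safeguard is absent from the readable text is good. Confidence in the exact order of steps is moderate, since it rests on two lists. The change is worth making because it is cheap and acts on the outcome the trial is meant to explain.

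**What to change.** **Before allocation.** State in Sections 9 and 11 that contact details are taken, the referral is confirmed where one is needed, and the DCOE appointment is booked with its date entered in REDCap, all before the REDCap allocation is opened. If no visit can be booked, enter the reason and a planned call-back date instead. Align Figure 1 with this order.

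**After allocation.** Booking first does not protect later calls. For patients not booked before discharge and for no-shows, apply the same fixed contact schedule in both arms. Log the attempts and the days to appointment, and report both by arm.

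**Outcome definition.** In Section 13, count attendance over all randomised patients, with never-booked patients counted as not attending, and say whether a rescheduled visit counts as attended.

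**Cost.** Protocol wording, a REDCap form order with a few added fields, and a short wait before allocation while the visit is booked. The sample size is not affected by the change of order. Because the 80% standard is now expressed over scheduled visits, it would have to be restated for the new denominator. Staff making later calls may still know the arm, so the change reduces the exposure without removing it.

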60-minute calibration period. They will be instructed to wear the CGM for two weeks continuously (including during sleep and hygiene), although they will also be advised that they can remove the sensor at any time if it causes any discomfort or distress. Subjects will not be removed from the study if they chose to remove the CGM. Participants will receive an informational sheet that explains the basic functionality of the CGM and lists Study Staff contact information in the event that they have questions about the CGM or its readings.

→ **Documents:**

- **CGM Information for enrolled patients (CGM arm only)**

- **Mobile Reader (CGM Arm only):** Study Staff will set up the Libre dedicated reader for subjects. Study Staff will demonstrate the features and use of the device and provide participants with an informational sheet that explains how and when to use the reader. Currently, Abbott, the company that manufactures the Libre 2 CGM system, is developing a mobile phone-based app to replace the reader. This app is under FDA review but is not yet approved. If it is approved between now and the end of enrollment, we will give participants the choice of using either the designated reader or their phone, if they possess a compatible phone.

→ **Documents:**

- **CGM Information for enrolled patients (CGM arm only)**

- **Education on managing out of range blood sugars:** All patients will receive information on how to respond to out of range blood sugars and emergency contact information

→ **Documents:**

- **Information sheet: Hyperglycemia**
- **Information sheet: Hypoglycemia**

- **Initial questionnaires: Patients will be administered** the five-question Problem Areas in Diabetes (PAID) scale as well as the 17-question Diabetes Distress Scale (DDS), which produces a total score and four subscale scores (emotional burden, regimen distress, physician distress, and interpersonal distress). Finally, patients will be administered several supplemental questions pertaining to their perceptions of their healthcare and barriers to obtaining optimal glycemic control.

→ **Paper Log:** Study Staff will administer these questionnaires on tablets shared with patients

▪ **Documents:**

- » **Problem Areas in Diabetes (PAID-5) scale/Diabetes Distress Scale and supplemental questions**

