14. PROVISIONS TO MONITOR THE DATA TO ENSURE THE SAFETY OF SUBJECTS*

In accordance with **HRP-801 Prompt Reporting Requirements**, any unanticipated adverse events will be reported and the PIs will closely monitor all aspects of the study.

The PIs will be responsible for monitoring adverse events during the study. If an adverse event occurs, their role will be to identify the concern, to develop an appropriate response to alleviate or minimize any adverse event, and to ensure that the adverse event is reported in a timely manner to the appropriate authority. Participants will be monitored for the occurrence of any

undesirable experience or unanticipated benefit. Events may occur during recruitment, during home CGM use, and during the initial follow-up visit. We anticipate that these effects will be limited. We will assess whether an undesirable experience (adverse event) occurred and will record details of all adverse events on an adverse event case report form. We do not anticipate that any serious adverse events (death, life threatening illness, new serious or permanent disability) will occur. However, should such an event occur, we will report the event within 24 hours to the University of Massachusetts Medical School (UMMS) Institutional Review Board.

The adverse event case report form will include a description of all undesirable experiences, required interventions, and an assessment of the participant after the event if possible. An estimate of the extent of injury and prevention strategies will be reported. The principal investigators will classify the relationship of the study protocol to the event as follows:

- Not related: The event is clearly related to factors not related to the study protocol.
- Remote: The event was most likely related to factors not related to the study protocol.
- Possible: The event follows a reasonable temporal sequence associated with participating in the study and/or is consistent with events related to the study protocol but is possibly related to factors such as the participant's clinical state.
- Probable: The event follows a reasonable temporal sequence associated with participating in the study and/or is consistent with events related to the study protocol and cannot be reasonably explained by factors such as the participant's clinical state.

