- The CGM is comfortable to wear. Local reactions are rare and generally mild. If a participant no longer wishes to use or wear the CGM s/he can simply remove the sensors to truncate data collection while still being a participant in the study. We consider this risk to be minimal.

- **Psychological Effects of CGM**

- Participants in the study may develop increased stress or awareness of their blood sugar as a response to the flow of data from the CGM. They may seek care or adjust their treatment regimen (correctional insulin, for example) based on CGM values. To mitigate this type of risk, all subjects will be supplied with extensive written information on how to manage hypo- and hyperglycemia, including clear instructions to check a finger-stick blood sugar level if there is any question of CGM inaccuracy, and will have the contact information for the study team if they have questions or concerns about the CGM or its readings. We have classified this risk to be minimal.
- An endocrinologist will be “on call” 24 hours a day, 7 days a week, and the study pager number will be provided to all participants. The study pager will be carried during business hours by a study team member, who will pass all medical calls to the on-call doctor. After hours, the on-call endocrinologist will carry the pager. If subjects encounter a blood sugar value or other adverse event that they need assistance with, they will be encouraged to call their primary care physicians. If they are unable to reach their PCPs or don’t have one, they will have the ability to page the provider on call, who will provide appropriate clinical guidance as to how to manage the adverse event. The provider on call will be a qualified endocrinologist who will be able to provide counseling on managing out of range blood sugars. If the complaint is too acute or complex to be managed on the telephone, the patient will be referred to the emergency department.
- The CGM sensor to be used in the proposed study is a commercially available device and will be used to obtain patterns in blood glucose monitoring. The Libre,

made by Abbott, does not qualify as an implant or life-sustaining device, nor does it pose a serious health risk to study participants. Because of this, the Libre CGM meets requirements for a Non-Significant Risk Device under FDA 21 CFR 812.3(m).

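### The plan undertakes to record all adverse events but schedules no adverse-event enquiry for anyone, and the planned no-show contact omits one

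*Combined protocol and SAP*

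**What the plan says.** Section 14 makes a broad commitment: "We will assess whether an undesirable experience (adverse event) occurred and will record details of all adverse events on an adverse event case report form". It names three periods in which events may arise (recruitment, CGM wear at home, the first follow-up visit) and defines severity grades for both groups. It gives no time, wording or form of contact for asking.

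Section 10 first says that the study records no primary or secondary safety measures. It then lists some: device questions or concerns up to the two-week appointment, reported high or low glucose values, and return visits or hospitalizations in the two weeks after enrollment.

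After ED discharge the one scheduled visit is Visit #1, at about day 14 to 21 (Sections 9 and 11), and the CGM download is listed under it. For no-shows, Section 11 has assistants reach out to "subjects who miss their follow-up appointment to (1) help them reschedule and (2) ask that they fill out the post-intervention questionnaire". Section 11 describes the questionnaire set, at baseline, as PAID-5, the DDS and "several supplemental questions pertaining to their perceptions of their healthcare and barriers to obtaining optimal glycemic control". The six-month step is a chart extraction without patient contact.

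Section 16 covers subjects who need help with a glucose value or other adverse event: "they will be encouraged to call their primary care physicians". If that physician cannot be reached, or there is none, "they will have the ability to page the provider on call". The same section says that "the study pager number will be provided to all participants".

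**The concern.** An undertaking to record all adverse events needs a means of finding them. Here the means are the chart, whatever the subject volunteers, and whatever comes up at the visit. The events most likely to escape the chart include several that Section 16 itself lists as risks of the device: skin reactions at the sensor site, distress at abnormal values and confusion about what to do with them.

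The visit matters because attending it is a primary outcome, and the hypothesis is that CGM raises attendance. If part of the safety record leans on the visit, its completeness leans on something the intervention is meant to change. The CGM arm also has extra contact with staff, through its information sheet and the return of the reader.

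Two features make a gap harder to repair. There is no data safety monitoring board (Section 14), so the investigators' own record is the safety oversight. And contact details are deleted once a participant's data collection is complete and the biosensor is returned (Section 26).

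**Working it through.** **Step 1. Which events depend on what.** Setting Sections 10, 11, 14 and 16 side by side:

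- ED visits and hospitalizations charted in the health record: found by the chart query, whether or not the subject attends.
- Device concerns and glucose events that the subject chooses to report: they can reach the study by pager or staff contact, without attendance.
- Glucose events handled by a primary care physician: no route from that physician to the study team is described. They are found if charted in the system queried or if the subject mentions them.
- Sensor-site reactions, confusion over readings and glucose events managed at home, if not volunteered: no scheduled enquiry is described. The visit is the only scheduled occasion on which they might come up.
- Distress: the DDS and PAID-5 go to no-shows too, but they measure diabetes distress in general and are not described as recording adverse events.

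**Step 2. Where the attendance values come from.** Section 13 tests a single proportion in the CGM group against 0.80, with 0.67 as the alternative, one-sided alpha 0.025 and 80% power:

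n = [(1.960 × √(0.80 × 0.20) + 0.842 × √(0.67 × 0.33)) / 0.13]² = 82.35, rounded up to 83.

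This reproduces the plan's 83. It also shows what 0.67 is: the alternative in a one-sample test within the CGM group. The plan states no attendance rate for the control arm.

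**Step 3. How many miss the scheduled visit.** Per 100 subjects: 100 × (1 − 0.80) = 20, and 100 × (1 − 0.67) = 33. These are upper figures for subjects never seen, because the first purpose of the no-show contact is to rebook.

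**Step 4. What that could do, as illustration only.** Assume an event that can occur in both arms, is found only at the visit, is asked of every attender, and has a risk unrelated to attendance. Captured events per 100 = 100 × risk × attendance.

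- Equal attendance: the between-arm ratio is 1.00, and 20% (at 0.80) to 33% (at 0.67) of such events are lost in each arm.
- Attendance 0.80 with CGM and 0.67 without (assumed): 20 + 33 = 53 of 200 miss the visit, and equal true risks appear as a ratio of 0.80 / 0.67 = 1.19. At assumed true risks of 5%, 10% and 20% the captured counts per 100 are 4.0 against 3.35, 8.0 against 6.7, and 16.0 against 13.4.

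For scale, at an assumed risk of 15% the captured rates are 12.0% and 10.05%, a gap of 1.95 points. With 100 per arm its standard error is √(0.12 × 0.88/100 + 0.1005 × 0.8995/100) = 0.044, or 4.4 points. Such a distortion would be lost in sampling noise.

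Sensor-site events cannot occur in controls, so no between-arm ratio applies to them. For these the issue is an undercount of the absolute rate in the CGM arm.

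**The case against.** There are several good points in the plan's favor.

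- A reader might infer that attenders are asked about adverse events and no-shows are not. The documents do not show this. No section says that adverse events are asked about at Visit #1, and the contents of the visit form are not given. The questionnaire items are not reproduced either, so the absence of an adverse-event item is an absence from the description only. This defeats a proven contrast between attenders and no-shows. What remains is that no enquiry is specified for anyone.
- A reader might infer that safety capture as a whole depends on attendance. It does not. The chart query, the round-the-clock pager, the staff contact details and the follow-up telephone call allowed for where necessary (Section 11) all work without a visit. But the pager and contact details rely on the subject to speak up, and the call has no stated safety content.
- A reader might take 1.19 as the expected bias. It rests on an assumed control-arm attendance and on capture at the visit alone, and Section 13 plans no between-arm analysis of adverse events that it could bias.
- A reader might see the instruction to call the primary care physician as routing events away from the study. It concerns where a subject seeks help and does not limit what the study records. The remaining gap is only that nobody is tasked with asking about such events afterwards.

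It is also fair that this is a short study of a commercially available device that the protocol classes as non-significant risk. That limits how serious the gap is. It does not remove the commitment in Section 14.

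**Conclusion.** The point holds in a limited form. Section 14 says the investigators "will record details of all adverse events on an adverse event case report form", and Section 10 lists device concerns and reported glucose events as safety measures, but no scheduled enquiry is specified for any subject and the no-show contact as written does not include one. Events that are neither charted nor volunteered therefore rest on the visit or on spontaneous report.

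At the plan's own attendance values, 20 to 33 per 100 would miss the scheduled visit, fewer after rescheduling. Capture could differ by arm if CGM changes attendance, but the documents do not allow the size, or even the presence, of such a bias to be established. The 1.19 ratio should be dropped or shown only as an illustration. The primary analyses are unaffected. This is an inexpensive improvement to safety data collection and worth making.

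**What to change.** Write one short adverse-event script and use it in both arms, at Visit #1 and as a third purpose of the no-show contact already planned in Section 11. If the visit form already holds such questions, use those. For both arms the script should cover high or low glucose events and any contact with a primary care physician, ED, emergency medical services or hospital, including events a primary care physician has already dealt with. Sensor-site and removal items go to the CGM arm only.

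Report adverse-event counts by arm together with the number of subjects asked and not asked, so that readers can judge completeness. Reconcile the two safety statements in Section 10, which cannot both stand as worded. The change concerns data collection only and leaves the instructions on where subjects seek help as they are.

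The cost is a few added questions and a short protocol change, with no new visit or staff. The contact becomes slightly longer, and the recorded adverse-event count will probably rise.
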